Email Campaign to Encourage Patients to Complete Sign-up Process for Geisinger's Patient Portal

NCT04332614

April 5, 2021

Study Protocol

Purpose

The purpose of the current study was to assess what kind of messaging improves the effectiveness of an email campaign targeted at enrolling patients into Geisinger's online patient portal, called myGeisinger. Currently, Geisinger sends an email every month to patients who have started but not completed the enrollment process (they have had an activation code generated but have not yet used that code to enroll). This study A/B tested 5 email messages to assess if they performed better than the current standard email message.

Background

In order to enroll in the myGeisinger patient portal, an activation code has to first be generated for a patient, which the patient subsequently uses to enroll in the portal. This code can be requested by the patient or generated by healthcare staff. Any patient who has had an activation code generated but has not yet enrolled is assigned a myGeisinger status of "Pending." Every month, patients with this status are sent an email encouraging them to enroll.

Method

Sample

The study population consisted of patients aged 18-88 who had an email address on file, a myGeisinger status of "Pending", and had not received emails from this monthly myGeisinger marketing campaign within the last 2 months. These eligibility criteria were used to match the ongoing marketing campaign already in place.

Based on the above criteria, N = 14,099 patients were randomized to a study condition and sent an email on April 6, 2020. Electronic Health Records for these patients were subsequently examined ~1 week and ~1 month after the campaign. We were only able to match unique records for 13,523 patients after ~1 week and for 13,344 patients after ~1 month, which served as the final sample for those respective analyses.

Intervention

Patients were randomly assigned to receive one of six emails. Each email intervention is named and described in the pre-registration under "Groups and Interventions." The precise email content is included in the Appendix below.

Outcomes

As described in the "Outcome Measures" section of the pre-registration, three outcome measures were assessed: Email opened, Link clicked, and Enrollment. The main purpose of examining *Email opened* was to evaluate the impact of the subject line; therefore, all patients whose emails were not delivered (i.e. bounced) were excluded from this analysis. The main purpose of *Link clicked* and *Enrollment* was to evaluate the impact of the full email (subject line and body); therefore, these outcomes were only assessed among patients who opened the email.

Data Extraction

The goal of this study was to evaluate outcome measures both 1 week and 1 month after the launch of the intervention. Technical issues resulted in delays in these data extractions. In addition, Enrollment data resided in a different database than the remaining email engagement data and was therefore extracted separately and subject to different delays. Below is the exact timeline of data extraction:

04/14/20 [08 days post-launch]: “1-week” engagement data

04/16/20 [10 days post-launch]: “1-week” enrollment data

05/08/20 [32 days post-launch]: “1-month” enrollment data

05/11/20 [35 days post-launch]: “1-month” engagement data

Statistical Analysis Plan

The primary questions of interest were whether each of the high-level interventions – less-is-better, social proof, or endowment – performed better than the standard email, which served as the control group. This was evaluated for all three outcome measures using a logistic regression (a generalized linear model with a binary distribution and log-link function) with the Standard Email condition dummy coded as the reference level. This dummy coding allowed for the comparison of each high-level intervention vs. control within a single model.

A secondary question of interest was: which less-is-better condition – provider communication, managing appointments, or medical information access – performed best? This was evaluated for all three outcome measures using a logistic regression (a generalized linear model with a binary distribution and log-link function). Each pair-wise comparison was evaluated with the appropriate correction for multiple corrections using a Tukey's test.

For both evaluations described above, a primary analysis was conducted for the outcome approximately 1 week after the intervention, and a secondary analysis was conducted approximately 1 month after the intervention. See the *Data Extraction* section of the *Study Protocol* above for the exact time frame.

For all tests, odds ratios (ORs) were calculated, along with 95% confidence intervals (CIs); two-tailed p-values < 0.05 were used to determine statistical significance.

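### As written, the sample for every outcome depends on a record match made after randomization, although opens and clicks come from a separate engagement database

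*Combined protocol and SAP*

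**What the plan says.** The Sample section states that 14,099 patients were randomized and emailed. It continues: "Electronic Health Records for these patients were subsequently examined ~1 week and ~1 month after the campaign". Directly after, it says "We were only able to match unique records for 13,523 patients after ~1 week and for 13,344 patients after ~1 month". Of these two matched sets it adds: "which served as the final sample for those respective analyses". One count is given per time point, and no outcome is set apart.

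The Outcomes section adds a restriction to each outcome. For Email opened, "all patients whose emails were not delivered (i.e. bounced) were excluded from this analysis". For Link clicked and Enrollment, "these outcomes were only assessed among patients who opened the email". Both restrictions are explained by what the outcome is meant to measure, and neither mentions a record match.

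The Data Extraction section says "Enrollment data resided in a different database than the remaining email engagement data" and "was therefore extracted separately and subject to different delays". Engagement data were pulled on days 8 and 35 after launch, enrollment data on days 10 and 32.

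For the primary comparisons the Statistical Analysis Plan says "This was evaluated for all three outcome measures using a logistic regression", and it does the same for the comparison among the three less-is-better emails. Analyses at about 1 week are primary and those at about 1 month secondary. Nowhere is there a reason for non-matching, a count of unmatched patients by email, or a sensitivity analysis.

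**The concern.** Patients appear to be removed after randomization by a condition that two of the three outcomes, as described, do not need. Whether an email was opened or a link clicked is held in the engagement data, so a failed match to a health record need not make that outcome unknown. The number matched also falls from the first time point to the second, so the match reflects the state of the records after randomization and is not a fixed baseline trait.

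Two things are at stake. The comparison no longer rests on everyone randomized, which opens the way to selection bias. And a reader cannot tell who was analysed for which outcome, because the only counts given are upper limits, before bounced emails or non-openers are removed.

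**Working it through.** The matched counts are observed numbers, so there is no planned figure to reproduce. The extraction days do check: from 6 April 2020, the dates 14 April, 16 April, 8 May and 11 May fall on days 8, 10, 32 and 35.

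**1. Patients dropped** (counts from the Sample section)
- About 1 week: 14,099 − 13,523 = 576; 576/14,099 = 4.09%.
- About 1 month: 14,099 − 13,344 = 755; 755/14,099 = 5.35%.

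**2. Change between time points**
- Fewest patients matched at 1 week but absent at 1 month: 13,523 − 13,344 = 179 (1.3% of 13,523).
- Smallest possible overlap: 13,523 + 13,344 − 14,099 = 12,768. The most that can be absent is therefore 13,523 − 12,768 = 755 (5.6%).
- Any enrollment already recorded for these 179 to 755 patients is left out of the 1-month result. How many of them opened the email or had enrolled is not given, and the number of enrollees could be zero.

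**3. Precision, if the loss is even over arms and outcomes (assumption)**
- Width of a log odds ratio interval relative to no loss: √(14,099/13,523) = 1.021 and √(14,099/13,344) = 1.028.

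**4. When exclusion distorts a single-email odds ratio**
- Observed OR = true OR × (email/control match-rate ratio in patients with the outcome) ÷ (the same ratio in patients without it).
- If matching differs by arm only, for example 90.9% against 95.9% at both outcome levels, the factor is (0.909/0.959)/(0.909/0.959) = 1.000. Distortion requires matching to depend on the outcome differently by arm.

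**5. The less-is-better contrast is different, because it appears to pool three emails**
- Assumed illustration: three equal-sized emails with rates of 10%, 14% and 18%, and a control rate of 12%.
- Full matching: pooled rate 14%; OR = (0.14/0.86)/(0.12/0.88) = 1.194.
- Matching of 100%, 95% and 88%, unrelated to outcome within each email: pooled rate = (10 + 14 × 0.95 + 18 × 0.88)/(1 + 0.95 + 0.88) = 39.14/2.83 = 13.83%; OR = 1.177.
- Matching that depends on the email alone can therefore move this contrast, by changing the weights.

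**6. What is possible without assumptions about the unmatched**
- With matched rate p and unmatched share d, the rate in the full set lies between p(1 − d) and p(1 − d) + d.
- For an assumed p of 20%: 19.2% to 23.3% at d = 4.09%, and 18.9% to 24.3% at d = 5.35%. These are extremes for one arm, not estimates.

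**7. Counting unmatched openers as not enrolled**
- Match rate 0.9465 unrelated to arm and outcome, assumed control enrollment 30%, true OR 1.5 (enrollment 39.13% in the comparison arm): rates become 28.40% and 37.04%, OR = 1.483, a factor of 0.989.
- Match rates of 85% in enrollees and 98.5% in non-enrollees, the same in both arms: excluding the unmatched gives 1.50, which is correct. Counting them as not enrolled gives rates of 25.5% and 33.26%, OR = (0.3326/0.6674)/(0.255/0.745) = 1.456.
- A difference between the two analyses would therefore not prove that the exclusion caused bias.

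**The case against.** The strongest reply is that this is unclear reporting and not a demonstrated analysis choice. The sentence on matching follows directly from one about health records, so it may concern Enrollment only. The sets given under Outcomes also mean that 13,523 and 13,344 can hardly be the actual denominators of any outcome. That reading is possible, but it is not stated. Under it the denominators for opens and clicks are still missing.

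A reader might infer that patients were discarded needlessly for opens and clicks. The documents do not establish this. They give no reason for the failed matches, they do not say whether the match was needed to attach the assigned arm or remove duplicates in the email data, and they refer to the pre-registration for the outcome measures. This part of the objection stands.

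It also stands that the losses are openly disclosed and that the cost in precision is small. Finally, counting week-1 enrollees in the main 1-month analysis may look like an obvious repair. It would admit otherwise unmatched patients only if they had enrolled, which creates a new selection problem.

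**Conclusion.** The point holds as a gap that should be closed. Read literally, the protocol applies a match made after randomization to all three outcomes at both time points, removing 4.1% of randomized patients at the primary time point and 5.4% at the secondary one from the starting set. For opens and clicks, no reason for this is given. The loss for each outcome cannot be computed, because counts of bounced and opened emails are not given.

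A reader might go further and infer that the odds ratios are biased. The documents do not support that: nothing shows that matching depended on the outcome differently by arm. Nor does the disclosure rule it out. If the loss is even, the consequence is intervals 2.1% and 2.8% wider. The size of any bias cannot be computed. Unmatched counts by email cannot settle the question for single-email contrasts, but they do bear on the weights in the pooled less-is-better contrast. Confidence is moderate, because the intended scope of the match is not stated.

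**What to change.** - State which outcomes the record match applies to, and the denominator for each outcome and time point.
- Analyse Email opened in all randomized patients whose email was delivered, and Link clicked in all openers, regardless of record match, provided the assigned arm can be linked to the engagement data. If it cannot, state that as a limitation.
- For Enrollment, keep matched openers as the main analysis at each time point. Do not carry 1-week enrollees forward into the main 1-month analysis.
- Report unmatched counts for each of the six emails, with reasons.
- Add an Enrollment sensitivity analysis at both time points that keeps unmatched openers under stated assumptions, for example not enrolled unless already recorded as enrolled at about 1 week. Present it as a range beside the main result, not as a test of whether the exclusion caused bias.

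The cost is a modest re-analysis of existing files and a table of denominators. It depends on the assigned arm and a patient key having been kept, which the documents do not say.

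### Link clicked and Enrollment are compared only among patients who opened the email, so the comparison is no longer randomized and can rank the better email as worse

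*Combined protocol and SAP*

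**What the plan says.** The Purpose section frames the trial as finding out "what kind of messaging improves the effectiveness of an email campaign targeted at enrolling patients". Under Intervention, "Patients were randomly assigned to receive one of six emails".

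The Outcomes section gives the three outcomes two different analysis sets:

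- For opening: "The main purpose of examining *Email opened* was to evaluate the impact of the subject line". Bounced emails are left out, so the denominator is delivered emails.
- For Link clicked and Enrollment, the aim was "to evaluate the impact of the full email (subject line and body); therefore, these outcomes were only assessed among patients who opened the email".

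The Statistical Analysis Plan applies the same kind of logistic model to all three outcomes, with email condition as the only term described. It mentions no adjustment for differences between openers, no sensitivity analysis, and no analysis of clicks or enrollment in all delivered or all randomized patients.

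The Data Extraction section shows that engagement and enrollment were read on different days: day 8 and day 10 for the one-week analysis, and day 35 and day 32 for the one-month analysis ("05/11/20 [35 days post-launch]: “1-month” engagement data").

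**The concern.** Randomization makes the six groups alike when the emails are sent. It does not make the openers alike. If one subject line attracts people whom another does not, the two sets of openers differ in motivation before anyone reads the body. A difference in enrollment between them then mixes the effect of the email with the effect of who was drawn in.

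The stated reason also works against the choice made. The subject line acts by getting the email opened. Once only openers are compared, the number of extra patients it brought to the body no longer counts. The restricted analysis therefore cannot measure the joint effect of subject line and body that the plan gives as its reason. Any enrollment by a patient not recorded as an opener is dropped as well.

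Enrollment is what the campaign is for. A subject line that brings in additional, less motivated readers lowers the rate among openers even while it adds enrollments in total. The sponsor could then judge the more productive email to be the worse one.

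**Working it through.** The plan has no sample-size, power or rate figure to reproduce. Its extraction days are correct: counted from 6 April 2020, 14 April, 16 April, 8 May and 11 May are days 8, 10, 32 and 35.

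**Inputs from the documents.** 14,099 patients randomized to six emails, three of them less-is-better; two-sided 0.05.

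**Assumptions.** Equal allocation, since no ratio is stated: 14,099 / 6 ≈ 2,350 per email, all treated as delivered. The email bodies have no effect. Enrollment occurs only among openers. All open and enrollment rates are assumed.

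**Identity.** Enrollments per delivered email = open rate × enrollment rate among openers. So the ratio of openers-only rates equals the ratio of enrollments per email divided by the ratio of open rates. With opens of 20% and 25% the second ratio is 1.25. An email yielding anything less than 25% more enrollments per patient therefore shows a lower rate among openers.

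**Worked example.** Control open rate o = 0.30, gain g = 0.06, habitual openers enroll at h = 0.06, extra openers at x = 0.01.

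| Analysis set | Control | New email | OR |
|---|---|---|---|
| Openers only | h = 6.00% | (o·h + g·x)/(o + g) = 0.0186/0.36 = 5.17% | 0.85 |
| All delivered | o·h = 1.80% | o·h + g·x = 0.0180 + 0.0006 = 1.86% | 1.03 |

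For pooled less-is-better against control, the openers number about 3 × 2,350 × 0.36 = 2,538 and 2,350 × 0.30 = 705. A two-proportion test (normal approximation, pooled variance) then declares the new emails significantly worse about 15% of the time. The nominal rate in that direction is 2.5%.

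**Range.** Open rates of 20, 30 and 40%, gains of 3, 6 and 10 points, and enrollment pairs (habitual, extra) of (6%, 1%), (6%, 2%), (10%, 2%) and (10%, 5%) make 36 combinations.

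- Openers-only OR: 0.71 to 0.96.
- All-delivered OR: 1.01 to 1.26.
- Chance of a false significant 'worse' for pooled less-is-better: 5% to 50%, median about 13%. With unpooled variance the range is 5% to 43%.

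**A second model.** Suppose 20% of patients are motivated, always open, and enroll at 20%. The others enroll at 5% if they open, and the subject line raises their opening from 6.25% to 18.75%.

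- Opens: 0.20 + 0.80 × 0.0625 = 25%, against 0.20 + 0.80 × 0.1875 = 35%.
- Enrollment per patient: 0.040 + 0.05 × 0.05 = 4.25%, against 0.040 + 0.15 × 0.05 = 4.75%; OR 1.12.
- Among openers: 4.25/25 = 17.0%, against 4.75/35 = 13.6%; OR 0.77.

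The direction reversed in all 18 variants of this model that were tried.

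**Boundary cases.**

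- If opens are equal (25% in both arms) and the same kinds of patient open, both ORs are 1.00 and there is no bias.
- If extra openers enroll at the same 20% as the rest, with opens of 25% and 35%, the openers-only OR is 1.00 while the rates per patient are 5.0% and 7.0% (OR 1.43). The planned analysis then misses a real benefit.

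**Dates.** At one month, a patient first opening on days 33 to 35 joins the denominator after enrollment was last read on day 32. At one week, a patient who first opens and enrolls on days 9 or 10 is left out.

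**The case against.** Nobody can dispute that opening is post-randomization or that no fuller analysis is planned. The arguable points concern size and remedy.

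- **The direction is built into the assumptions.** Every combination in the grid has the new subject line raising opens and the extra openers being less motivated, so reversal must follow. This is fair. The figures show what can happen and do not estimate what did. The 50% is a single extreme combination (20% opens, 10-point gain, 10% against 2%).
- **The fix seldom proves an email better.** In the worked example the all-delivered test finds a significant benefit only about 4% of the time (median about 5% over the grid), and the planned test does not report 'worse' about 85% of the time. This also stands. The main gain is removing a biased comparison; power to find a winner stays low when the true difference is small.
- **A reader could multiply open rate by openers-only rate.** This works for clicks if counts are reported. It cannot recover enrollments by non-openers, and the plan attaches no test or interval to the product.
- **Enrollments by non-openers are set to zero in the calculation.** Correct. Enrollment unrelated to the email would pull the all-delivered ORs towards 1.
- **Some arms may share a subject line.** The Appendix and pre-registration content is not available here. Arms with the same subject line, possibly among the three less-is-better emails, could be compared fairly among openers. Measuring the subject line through opening makes sense only if it differs between at least some arms.
- **The date mismatch is small.** It is the same in every arm. At the primary one-week time point enrollment was read after engagement, so every recorded opener had been followed. It is a side issue.

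**Conclusion.** The concern holds. The plan conditions two of its three outcomes on an event that it treats elsewhere as an effect of the randomized subject line, and the reason it gives calls for the opposite choice. As written, Enrollment has no randomized comparison at all.

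The size in this trial is unknown because no open, click or enrollment rates are stated. Under identical bodies and a subject line that draws in less motivated readers, the planned OR falls to 0.71 to 0.96 while the all-delivered OR is 1.01 to 1.26. A false finding of 'worse' then occurs in 5% to 50% of trials for pooled less-is-better against control. The bias vanishes only if the subject line does not change who opens. This must be fixed before the Link clicked or Enrollment results are read as effects of the emails.

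**What to change.** Make the primary analysis of Link clicked and Enrollment use every randomized patient whose email was delivered, the denominator already used for Email opened. All randomized patients would serve equally, and are the safer set if bounces differ by arm. Count non-openers as not having clicked, and take enrollment from the record whether or not the email was opened. For Enrollment this also removes the dependence on mismatched extraction dates.

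Keep the openers-only analysis as a secondary descriptive result, with a statement that it is not a randomized comparison. Arms shown to share a subject line may be noted as an exception.

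The document is dated a year after the emails were sent and is written in the past tense. The change should therefore be reported as post hoc, and as a departure from the pre-registration if that specified openers only.

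The cost is revised wording, that disclosure, and a re-run on data already extracted. Absolute rates will be smaller because the denominator is larger. The fix does not address the unmatched records (14,099 − 13,523 = 576, or 4.1%, at one week; 14,099 − 13,344 = 755, or 5.4%, at one month), which are a separate loss.

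### The 1-month Enrollment analysis counts openers up to day 35 but sees enrollment only to day 32, so patients who first opened on days 33-35 have no observable outcome (minor)

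*Combined protocol and SAP*

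**What the plan says.** The Sample section fixes day 0: "patients were randomized to a study condition and sent an email on April 6, 2020". On Link clicked and Enrollment, the Outcomes section says that "these outcomes were only assessed among patients who opened the email".

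The Data Extraction section explains that "Enrollment data resided in a different database than the remaining email engagement data and was therefore extracted separately and subject to different delays". It then lists four dates:

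- 1 week, opening and clicking: "04/14/20 [08 days post-launch]: “1-week” engagement data"
- 1 week, enrollment: "04/16/20 [10 days post-launch]: “1-week” enrollment data"
- 1 month, enrollment: "05/08/20 [32 days post-launch]: “1-month” enrollment data"
- 1 month, opening and clicking: "05/11/20 [35 days post-launch]: “1-month” engagement data"

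The Statistical Analysis Plan makes 1 week the primary and 1 month the secondary analysis. On timing it says only: "See the *Data Extraction* section of the *Study Protocol* above for the exact time frame". It gives no common cut-off, no truncation of either extract by event date, no rule on the order of opening and enrollment, and no sensitivity analysis.

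**The concern.** For Enrollment, membership of the denominator is decided in one database and success in another. At 1 month the denominator stays open three days longer than the numerator. Patients who first opened in those three days can only appear as failures, unless they had already enrolled before opening, in which case the opened email did not lead to the enrollment. Either way they say nothing about what the analysis is meant to measure, the effect of the full email on people who opened it.

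At stake is a slightly low 1-month Enrollment proportion and, if messages differ in how many people open them very late, a shift in the odds ratio. Only Enrollment at 1 month is affected. Email opened and Link clicked both come from the engagement extract and share one cut-off.

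**Working it through.** **Day counts.** From 6 April 2020: 14 April is day 8, 16 April is day 10, 8 May is day 32 and 11 May is day 35. All four agree with the document.

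**Gap between cut-offs (enrollment day minus opening day).**

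- 1 week: 10 − 8 = +2. Every counted opener is followed for at least 2 days after opening.
- 1 month: 32 − 35 = −3. Anyone first opening on days 33, 34 or 35 is counted with no follow-up after opening.

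**Effect on the proportion.** Let p be the proportion enrolled among those who opened by day 32, s the share of day-35 openers who first opened on days 33-35, and q the proportion of those late openers who had enrolled by day 32. Then

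observed proportion = p(1 − s) + qs.

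This is below p whenever q < p. With q = 0 it is p(1 − s), a relative understatement of s. The documents give neither opening times nor enrollment rates, so s and p below are assumptions, and q is set to 0, which gives the largest understatement.

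**Odds ratio, equal late-opener shares.** Take 10% enrollment under control and 12% under intervention; the true odds ratio is (0.12/0.88)/(0.10/0.90) = 1.227.

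- s = 5% in both arms: observed 0.095 and 0.114, odds ratio (0.114/0.886)/(0.095/0.905) = 1.226.
- Shares from 0.5% to 5% in both arms all give 1.226-1.227.

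**Odds ratio, unequal shares, no true effect.** Take s = 5% under intervention and 2% under control.

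- p = 0.05: observed 0.0475 and 0.0490; (0.0475/0.9525)/(0.0490/0.9510) = 0.968.
- p = 0.20: observed 0.190 and 0.196; (0.190/0.810)/(0.196/0.804) = 0.962.

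**Odds ratio, unequal shares, true value 1.227 (10% against 12%).**

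| Control s | Intervention s | Observed odds ratio |
|---|---|---|
| 1% | 3% | 1.199 |
| 1% | 5% | 1.171 |
| 3% | 1% | 1.255 |

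The direction depends on which arm has more late openers.

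**Against sampling error.** Assume six equal arms of the 13,344 patients matched at 1 month (2,224 each), 15-50% opening (334 to 1,112 openers per arm) and 5-20% enrollment. For one message against control, the standard error of the log odds ratio is √[2/(np(1 − p))].

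- n = 334, p = 0.05: standard error 0.355; bias ln 0.968 = −0.033; ratio 0.09.
- n = 1,112, p = 0.20: standard error 0.106; bias ln 0.962 = −0.039; ratio 0.36.

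Even with the unequal 5% and 2% shares, the bias is 0.09-0.36 of a standard error.

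**The case against.** The strongest reply is that the mismatch is disclosed, three days long, confined to one of three outcomes at the secondary time point, and applied identically to every arm. Few people are likely to first open a single email a month after it was sent: opening spread evenly over 35 days would put only 3/35 = 8.6% in the last three, so a 5% share already implies little decay. The 5% against 2% scenario also needs a 2.5-fold difference between arms. All of this stands, and it is why the point is minor. Disclosure does not put the missing outcomes back, however.

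Two further points also stand. Short follow-up for the latest openers comes with any fixed cut-off among openers; the mismatch adds three days of openers with none at all. And enrollment before opening could count as success at either time point, because the plan sets no order for the two events.

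A reader might infer three stronger things that the documents do not support:

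- **That the 1-week analysis is wrong too.** It is not. Patients first opening on days 9-10 are absent from numerator and denominator alike, whether or not they enrolled, so the proportion among day-8 openers is undistorted. Cutting both variables at day 8 would exclude the same patients and discard follow-up at the primary time point.
- **That the odds ratios are biased because subject lines are expected to affect opening.** The Outcomes section supports a difference in whether patients open, not in how many first open on days 33-35.
- **That the mismatch spoils a comparison of 1-week with 1-month results.** The plan specifies separate analyses and makes no such comparison.

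**Conclusion.** The point holds for Enrollment at 1 month only, and it is minor. As written, the denominator includes patients first opening on days 33-35, for whom no enrollment after opening can be observed. This lowers the proportion by at most a relative s in each arm, and by less if some of these patients had already enrolled.

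With equal late-opener shares the odds ratio is essentially unchanged. With an assumed 5% against 2% and 5-20% enrollment, a true value of 1.00 is estimated as 0.96-0.97, or as its inverse, about 1.03-1.04, if the shares are reversed. These sizes rest wholly on assumed shares and rates. The conclusion also assumes that no unreported truncation by event date was made; the plan describes none and refers to the extraction dates for the time frame.

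**What to change.** Any one of these repairs the 1-month Enrollment analysis; the choice should be stated in the Statistical Analysis Plan with its cut-off days.

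1. **Day-8 openers with the day-32 enrollment extract.** Both already exist and no event dates are needed. Every counted patient has at least 32 − 8 = 24 days after opening. The cost is fewer openers: those first opening after day 8 are lost, as are any day-8 openers without a unique record at 1 month (matched totals fall from 13,523 to 13,344, a net 179).
2. **Exclude patients who first opened after day 32.** This keeps more openers but needs opening dates, which the documents do not say are held, and it leaves short follow-up for the latest openers.
3. **Analyse Enrollment in all randomized matched patients.** The opener denominator disappears, and the mismatch with it. The cost is a little more analysis and a change of question, from enrollment among openers to enrollment among those sent each message. Whether to condition on opening at all is a separate and larger matter that options 1 and 2 do not settle.

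Keep the 1-week pairing as it is. If the existing 1-month analysis is retained, report option 1 beside it as a sensitivity analysis.
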